In Colombia, the prevalence of hepatitis C among PWID has been measured locally in some cities of the country. The first measurement was carried out with the 2002 study in Bogotá. Later, in 2014 it was held in Bogotá, Pereira, Medellín, Cucuta and Armenia. The figures at that time already indicated a clear impact by this virus in this population. In Bogotá it went from 1.7% in 2002 to 6.7% in 2014. The cities with the lowest prevalence in 2014 were Cucuta with 21.4% and Armenia with 30.9%, while in Medellín the estimated prevalence It was 35.6% and in Pereira it was 44.4% (15). For 2021, the prevalence of hepatitis C was measured in Bogotá, Medellín, Santiago de Cali, the metropolitan area of Pereira-Dosquebradas, Medellín, Cucuta and Armenia (15,16). The results of prevalence of antibodies against hepatitis C were as follows: Cali with 80.2%, is the city with the highest reactivity, followed by Pereira and Dosquebradas with 71.4%, Armenia with 69.6% and Cucuta with 62.8% (15,16). In Medellín, antibody reactivity was found in 32.7% of PWIDs and in Bogotá in 10.7% of them. The comparison of the findings between this study and the CES University study in 2014 shows a slight reduction in the hepatitis C figures in Medellín, and an increase of several percentage points in Bogotá, Pereira –Dosquebradas, Cucuta and Armenia. There is no previous data on hepatitis C for Santiago de Cali.

With the promising effectiveness of antivirals to treat the infection and prevent transmission (17), WHO declared the intention to eliminate viral hepatitis by 2030 (18). Targets for ID: CO-US-987-7106 - Version May 2024

elimination include an 80% decrease in new HCV cases, 90% of infections diagnosed, 80% of infections receiving treatment, and 65% reduction in HCV-related deaths. However, most people with HCV are unaware of their status due to asymptomatic infection, low screening, and, among those screened, limited diagnosis and linkage to care (19,20). The lack of accurate national HCV surveillance systems, particularly for key populations such as PWID, contributes to the challenges of HCV control and elimination (21). Additional studies are needed to improve HCV screening, evaluation, and treatment to reduce the burden of HCV infection among PWID.

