To estimate the prevalence of hepatitis C antibodies through rapid test screening and identify the behaviors associated with infection in people between 18 and 65 years of age who inject drugs in the city of Armenia.

Specific objectives

- Estimate the size of the population of people who inject drugs in the city of Armenia.
- Estimate the prevalence of antibodies against HCV in PWID.
- Socio-demographically characterize the study population.
- Describe the epidemiological characteristics of PWID with positive antibodies for HCV.
- Identify behaviors associated with HCV infection among PWID.
- Determine the proportion of PWID with positive HCV antibodies and positive HCV viral load.
- To carry out an exploratory analysis of the association of positive cases and the different risk factors for HCV infection among PWID.
- To quantify how many PWID with positive viral load for HCV were able to access the management route and treatment.

B. METHODOLOGICAL APPROACH

Type of study

An anonymous, confidential analytical cross-sectional study will be carried out, in which the prevalence of hepatitis C will be estimated, the behaviors associated with the consumption of psychoactive substances by injection will be analyzed in people between 18 and 65 years old who inject drugs in the city of Armenia.

Population and sample

Population

The universe for this study was people between 18 and 65 years old who have injected drugs in the last six months in Armenia and the participants were selected through the implementation of the respondent-driven sampling (RDS).

Inclusion and exclusion criteria

Inclusion criteria

- Be between 18 and 65 years old.
- Having injected psychoactive substances in the last six months.
- Residing in the city or metropolitan area of study in the last six months
- Present the invitation coupon.
- Person with Colombian nationality, Venezuelan migrant population.

Exclusion criteria

- Person who, due to physical, cognitive or limitations derived from the use of psychoactive substances, is not able to answer the survey autonomously.
- Person who is in a state of consumption and is prevented from responding to the survey.
- Person who refuses to collaborate in the study.

Sampling frame

Statistical units

The statistical units of analysis, observation and sampling are the key population of Armenia.

Target population size

Sample sizes and precision for estimating a population proportion.

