Population size (for finite population correction factor or fcp) (N): 580¹

Hypothetical % frequency of the outcome factor in the population (p): 77.80%²+/-5

Confidence limits as % of 100 (absolute +/-%) (d): 5%

¹Patients treated at the Armenia City Listening Center between 2016-2023.

²Estimated based on the 2021 prevalence (62.80%), along with the growth speed of 5% per year.

Design effect (for group surveys-EDFF): 1

Sample size (n) for various confidence levels.

Interval Trust (%)	Size of the sample
95%	186
80%	98
90%	145
97%	213
99%	260
99.9%	331
99.99%	377

Sample size n = $[EDFF^*Np(1-p)] / [(d^2/Z^2(1-\alpha/2)^*(N-1) + p^*(1-p))]$

Source: Results from OpenEpi, version 3, the SSPropor open-source calculator

The sample size may vary by up to 10%, taking into account (i) the methodological adjustments that are made once the study begins, in which case the sample size will be adjusted.

Sample size 205 individuals.

Sample design

Due to the type of population (PWID), it is not possible to have a known sampling frame that allows designing a conventional probabilistic sample, so a chain reference sample will be taken based on those who respond (respondent driven sampling -RDS), a method that has proven its usefulness to access hard-to-reach populations (15,16). Respondent-driven sampling is a network-based sampling method, which makes it possible to draw statistically valid samples from previously unreachable groups. It is based on long referral chains and therefore several waves of recruitment. Likewise, several waves of recruitment make it possible to ensure that the final sample is independent of the seeds and this sample is similar to the population of the network from which the sampling was done (16). For example, in the prevalence study in 2021, the method estimated a population of 463 (95% CI: 431-497) people who inject drugs. Regarding completeness, through the RDS methodology, 53.4% of the population were identified and the method estimates that 80.19% of the population in the city of Armenia was identified³ (16).

The seeds are those leaders of the population who begin the information gathering process.

³<https://www.minjusticia.gov.co/programas-co/ODC/Documents/Publicaciones/Informe%20de%20Resultados%20de%20Investigaci%C3%B3n%20n%20PID%20Armenia-Cu%C3%81cuta%20Marzo%202022.pdf>

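### The planning prevalence starts from a 2021 figure that the background text gives for Cucuta, not Armenia, and the printed sample-size table does not follow from the stated 77.8%

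*Protocol*

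**What the plan says.** The study is confined to one city. The General objective concerns "people between 18 and 65 years of age who inject drugs in the city of Armenia", and the Sampling frame section says "The statistical units of analysis, observation and sampling are the key population of Armenia".

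Under Target population size, the protocol lists the inputs to a single-proportion calculation:

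- population size 580;
- "Hypothetical % frequency of the outcome factor in the population (p): 77.80" (per cent, followed by a ±5);
- "Confidence limits as % of 100 (absolute +/-%) (d): 5" (per cent);
- "Design effect (for group surveys-EDFF): 1".

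Footnote 2 explains the prevalence as "based on the 2021 prevalence (62.80%), along with the growth speed of 5% per year". The section then prints a formula with a finite population correction and a table of seven sample sizes, 186 at 95% confidence. It allows a variation of up to 10% and ends with "Sample size 205 individuals".

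The Problem statement and justification reports the 2021 antibody prevalence by city, including "Armenia with 69.6% and Cucuta with 62.8" (per cent).

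**The concern.** There are two separate faults in the same calculation.

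First, the 62.80% in footnote 2 is the number that the background text assigns to a different city. Armenia's number there is 69.6%. Either the calculation used the wrong city or the background text has the cities wrong.

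Second, the sample sizes in the table are not those that the printed formula gives for the printed prevalence.

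Prevalence in Armenia is the main quantity to be estimated, and the assumed prevalence drives both the sample size and the claimed ±5 points. As written, a reader cannot tell which 2021 figure belongs to the study city and cannot reproduce the table.

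**Working it through.** **Inputs.** From Target population size: N = 580, d = 0.05, design effect 1, p = 0.778. From the Problem statement: 69.6% (Armenia) and 62.8% (Cucuta).

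**Origin of 77.8%.** 62.8 + 3 × 5 = 77.8, which is three yearly steps of 5 percentage points (2021 to 2024). Relative growth does not give it: 62.8 × 1.05³ = 72.7. So the footnote's 5% per year means points, and the starting value is the one given elsewhere for Cucuta. The same rule from 69.6 gives 69.6 + 15 = 84.6.

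**The plan's own table.** The printed formula with design effect 1 is

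n = N·p(1−p) / [(d²/z²)(N−1) + p(1−p)], rounded up.

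At 95%, z = 1.96 and (d²/z²)(N−1) = 0.3768. With p = 0.778, p(1−p) = 0.172716, so n = 580 × 0.172716 / (0.3768 + 0.1727) = 182.3, that is 183. The plan prints 186.

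| Confidence level | Printed | p = 77.8% | p = 77.0% |
|---|---|---|---|
| 95% | 186 | 183 | 186 |
| 80% | 98 | 96 | 98 |
| 90% | 145 | 142 | 145 |
| 97% | 213 | 209 | 213 |
| 99% | 260 | 257 | 260 |
| 99.9% | 331 | 327 | 331 |
| 99.99% | 377 | 374 | 377 |

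At the stated 77.8% every row falls short of the printed value by 2 to 4 persons. At 77.0% all seven agree exactly. With d fixed at 5%, a search in steps of 0.01 point from 70% to 86% finds agreement only from 76.98% to 77.00%. Keeping p = 77.8% and shrinking d to between 4.936% and 4.938% also reproduces the table. With p = 77.8% and d = 5%, no whole N from 400 to 1199 and no design effect from 0.9 to 1.1 does. The final figure appears to be 186 × 1.10 = 204.6, rounded to 205.

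**What depends on the starting figure.** Half-width at n = 205 comes from solving the same formula for d (95%, N = 580, design effect 1).

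| Assumed prevalence | Required n | Half-width at 205 (points) |
|---|---|---|
| 62.8% (no growth) | 222 | ±5.3 |
| 69.6% (no growth) | 209 | ±5.1 |
| 77.8% (62.8% + 15 points) | 183 | ±4.6 |
| 84.6% (69.6% + 15 points) | 150 | ±4.0 |

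The required n falls to 205 at a prevalence of about 71.0%, so 205 delivers ±5 points only from there upward. In the printed formula the design effect multiplies n directly. The room left by 205 is therefore 205/182.29 = 1.12 at 77.8% and 205/149.02 = 1.37 (rounded down) at 84.6%.

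**The case against.** The case against accepts the contradiction and the arithmetic, and argues that little follows from them.

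- **The table gap is trivial.** It is 2 to 4 persons per row, always on the safe side, and most simply explained by entering 77 instead of 77.8. That is fair as to size. But a closed formula with whole-number output should agree exactly when the inputs are right, and here no row does. The explanation by 77% is likely but not proven. The alternative of a slightly smaller d fits only a very narrow window and is less plausible.
- **The protocol allows a band.** The prevalence is printed with ±5. If this is a tolerance on p, it spans 72.8% to 82.8%, for which the formula gives 200 and 160, both under 205. The ±5 may equally just repeat the precision. In neither reading does it settle which city the 62.8% belongs to, and 84.6% lies outside the band.
- **The no-growth rows are not what the protocol assumes.** This stands. With growth, every version stays under 205: besides 183 and 150, compounding at 5% gives 201 from 62.8% (72.7%) and 171 from 69.6% (80.6%). The no-growth rows show only how far the precision claim leans on the growth assumption. At 69.6% the miss is slight (5.07 points).
- **The design effect is a separate question.** Agreed. The limits above mark how far these figures reach; they are not evidence that 1 is wrong.

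**Conclusion.** The point holds as a minor error of fact and arithmetic. The protocol contradicts itself on the 2021 prevalence in its only study city, and that figure feeds directly into the sample size. The document alone cannot show which place is wrong. If 62.8% is Armenia's, the planning value stands and the background text is wrong. If 69.6% is Armenia's, the footnote's own rule gives 84.6% and a required size of 150.

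The table is also inconsistent with its stated prevalence, by 3 persons at 95% (186 against 183), in the conservative direction.

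Neither fault calls for a change in enrolment. Nor does this check establish that 205 is sufficient: every figure is conditional on N = 580, a design effect of 1 and, for the two growth cases, the assumed rise of 15 points.

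**What to change.** 1. Look up Armenia's 2021 antibody prevalence in the Armenia-Cucuta report already cited (reference 16), and correct either the Problem statement or footnote 2.
2. In footnote 2, name the city and state the growth as 5 percentage points per year from 2021 to 2024.
3. Rerun the table at the prevalence actually stated. At 95% this gives 183 for 77.8% if 62.8% is Armenia's, or 150 for 84.6% if 69.6% is.
4. Beside it, state the precision that 205 gives: ±5.3 points at 62.8%, ±5.1 at 69.6%, ±4.6 at 77.8% and ±4.0 at 84.6%. Say that these hold only for N = 580 and design effect 1.

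The cost is one look at a cited source, one corrected footnote or sentence, and one rerun of the calculator.

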In this sampling it is necessary to link the referral with the interviewee, which is achieved through coupons marked with the RDS code (unique number) that allows identifying all the referrals of a seed and therefore its social network. Likewise, the reference quota is controlled with a maximum number of coupons, which for this study would be three per interviewee, which allows limiting "recruiter" bias; coupons are an inclusion criterion that allows determining whether the person was eligible for participate and essential to preserve the link between referent and referred.

Respondents recruit their peers, as in network-based samples, and researchers keep track of who recruited whom and their number of social contacts. A mathematical model of the recruitment process then weights the sample to compensate for non-random recruitment patterns. This model is based on a synthesis and extension of two areas of mathematics, first-order Markov chain theory (i.e., sampling occurs with replacement, the sample becomes independent of the seeds). And biased network theory, which were not part of the standard toolset of mathematical sampling theory. The resulting statistical theory, called RDS, allows researchers to provide unbiased population estimates and measures of the precision of those estimates.

Variables

The dependent variable would be the identification of HCV antibodies, which is qualitative with nominal measurement as presence (positive) or absence of the virus (negative). The questions that will make up the survey will be the independent variables, whose nature is qualitative or quantitative and the measurement levels are nominal and ratio, such as age, number of times per day in which you inject, number of people with whom you have shared syringes and needles, injection equipment, number of casual or commercial couples, among others.

Collection of information and sampling procedure

Once approval has been obtained from the research ethics committee for this study, in the first phase people called seeds are selected, a record of the identified population will also be made, and the first part of the capture-recapture methodology will be applied. In the second phase of expansion, it is expected to recapture the population and estimate the population, with which the waves of the RDS methodology are carried out.

The researcher initially searches for individuals (called seeds) who belong to the population

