The RDS itself estimates the sampling errors described through measures such as homophily, heterophily, and proportional estimates of the population. Initially, homophily will be calculated, which describes the extent of the ties of the social network inside or outside it. The homophily/heterophily scale is between 1 and -1, where 1 indicates that all participants with certain characteristics invited someone with the same characteristics, while -1 indicates that all participants with a certain characteristic invite someone with one characteristic opposite or different; 0 (zero) was the point at which participants randomly invited other individuals from the population of all possible invitees.

The RDS technique uses the information available in the sample about the social network to obtain asymptotically unbiased estimators of the proportions of the population in the different groups in which they want to be characterized. These estimators are called population prevalence estimators.

Descriptive statistics (frequencies and percentages) will be estimated. For continuous quantitative variables, measures of central tendency (average and median) and measures of dispersion (variance, standard deviation) will be estimated.

A descriptive analysis of the characteristics of the population under study will be carried out, according to the socio-demographic variables: sex, age, educational level, stratum, insurance, in addition the prevalence of HCV and the proportions of the sample and the population will be obtained. according to the risk behavior variables associated with infections. All these analyzes are carried out by estimating the population with their corresponding 95% confidence intervals.

Possible relationships between sociodemographic variables, risk factors and documentation of positive antibodies for HCV will be explored. For this purpose, a bivariate analysis will be proposed using chi-square tests to explore the proposed associations. The test allows us to determine, for each pair of variables, the existence or not of the relationship through the difference between the value that should result if the two variables were totally independent, and the one observed in the data. The greater the difference, the greater the relationship between the variables.

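### The sample size uses a design effect of 1 for a weighted chain-referral sample, without justification, so the ±5 points at 95% confidence behind 186 and 205 is unsupported

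*Protocol*

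**What the plan says.** Under Target population size, the protocol sizes the study to estimate one proportion. The inputs are a population of 580, an expected prevalence of 77.80%, a half-width stated as "Confidence limits as % of 100 (absolute +/-%) (d): 5" (per cent), and "Design effect (for group surveys-EDFF): 1". A seven-row table follows, with 186 in the 95% row. The protocol then allows the size to vary by up to 10% for methodological adjustments and ends with "Sample size 205 individuals".

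The next section, Sample design, says that no frame exists for a conventional probability sample, and that "a chain reference sample will be taken based on those who respond (respondent driven sampling -RDS") instead. It adds that "A mathematical model of the recruitment process then weights the sample to compensate for non-random recruitment patterns", under a theory in which "sampling occurs with replacement, the sample becomes independent of the seeds". It also reports that in the 2021 survey "the method estimated a population of 463 (95% CI: 431-497) people who inject drugs". Coupon Registration requires each participant's network size to be recorded. The Data analysis plan says: "Initially, homophily will be calculated, which describes the extent of the ties of the social network inside or outside it".

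**The concern.** A design effect of 1 says that the estimate will have the variance of a simple random sample of the same size. The protocol describes a sample with two features that usually raise the variance above that: unequal weights, and dependence between recruiter and recruit, which homophily measures. No reason is given for 1, and no design effect is taken from the 2021 Armenia survey, which used the same method.

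The nearest thing to a defence is in the section on social support for respondents. It expects the incentives to keep the sample variance close to that of the population estimate without high homophily. It gives no figure and does not address unequal weights.

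Prevalence is the first element of the general objective, and the 5-point half-width is the only criterion used to choose the sample size. A reader will take ±5 points as the precision the study is planned to deliver.

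**Working it through.** **Inputs (Target population size).** N = 580, p = 0.778, d = 0.05, design effect (DEFF) = 1, z = 1.96 at 95%. Sample design supplies the alternative N = 463.

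**1. Reproduce the plan's figures.** The printed formula is

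n = DEFF·N·p(1−p) / [(d²/z²)(N−1) + p(1−p)].

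- With p = 0.778: 580 × 0.1727 / (0.3768 + 0.1727) = 182.3, so 183.
- With p = 0.77: 580 × 0.1771 / (0.3768 + 0.1771) = 185.4, so 186.
- All seven printed rows follow at p = 0.77. The values 185.4, 97.1, 144.2, 212.0, 259.9, 330.5 and 376.6 round up to 186, 98, 145, 213, 260, 331 and 377. The calculator was evidently run with 77%, a small difference.
- 186 × 1.10 = 204.6, so 205.

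There is no calculation slip. Both values of p are carried below.

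**2. How large a design effect does each size tolerate?** The 95% half-width is

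h = 1.96·√[DEFF·p(1−p)/n·(N−n)/(N−1)].

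The largest DEFF that keeps h at or below 5 points is:

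| n | Correction | p = 0.77 | p = 0.778 |
|---|---|---|---|
| 186 | N = 580 | 1.004 | 1.030 |
| 186 | N = 463 | 1.14 | 1.17 |
| 205 | N = 580 | 1.163 | 1.193 |
| 205 | N = 463 | 1.349 | 1.383 |
| 205 | none | 0.753 | 0.772 |

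The printed formula multiplies the already corrected n by DEFF, so it is less generous to 205 at N = 580: 205/185.4 = 1.105 and 205/182.3 = 1.125.

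The last row of the table matters because the theory cited in Sample design treats sampling as with replacement. Under that model no finite correction applies, and 205 people give 1.96·√(0.1727/205) = 5.7 points even at a design effect of 1.

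**3. Expected half-width at n = 205, p = 0.778.** The documents give no design effect other than 1, so 1.5 to 3 is an assumed range.

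| DEFF | N = 580 | N = 463 | No correction |
|---|---|---|---|
| 1 | 4.6 | 4.3 | 5.7 |
| 1.5 | 5.6 | 5.2 | 7.0 |
| 2 | 6.5 | 6.0 | 8.0 |
| 3 | 7.9 | 7.4 | 9.9 |

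**4. How readily could the slack be used up?** As an illustration only, assume zero homophily and DEFF ≈ 1 + CV² of the weights. The N = 580 limits of 1.163 and 1.193 correspond to weight CVs of √0.163 = 0.40 and √0.193 = 0.44. Suppose the sample splits into two equal halves with weights inverse to network size. The ratio of network sizes is then (1+CV)/(1−CV), or about 2.4 to 2.6. At N = 463 the ratio is 3.9 to 4.2.

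**5. What the plan would need at a larger design effect.** At p = 0.778 and N = 580, the printed formula asks for 274 at DEFF 1.5 and 365 at DEFF 2. If DEFF is applied before the finite correction, which matches the half-width equation in step 2, the figures are 237 and 278. All exceed 205.

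**The case against.** Several points on the other side are fair.

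- **The ±5 points belongs to 186.** The protocol attaches it only to the table row, and states no precision for 205. That is so, but 205 is 186 plus 10% and no other precision is given for it. The allowance is not described as a design-effect adjustment, and it covers only 1.10 to 1.12 by the printed formula.
- **The assumption is disclosed.** The value 1 is printed above the table. What is missing is a reason for it.
- **The slack depends on p.** Footnote 2 builds 77.8% on 62.80%, which the Problem statement gives for Cucuta; Armenia is given as 69.6%. Adding the same 15 points to 69.6% gives 84.6%, where 205 tolerates 1.58 (N = 580) or 1.83 (N = 463). With 69.6% and no growth the limits are 0.97 and 1.13. This stands as a caution: the narrow limits above hold for the protocol's stated p only. It does not rescue the assumption, since at 84.6% and N = 580 the half-width at a design effect of 2 is 5.6 points.
- **Recruitment is without replacement in practice.** Instructions for recruitment do not count people who have already taken part, and 205 is 35% of 580 or 44% of 463. The uncorrected figures therefore follow from the cited theory, not from the fieldwork. At p = 84.6% even the uncorrected half-width at DEFF 1 is 4.9 points. The protocol has to settle which applies.
- **The consequence is limited.** The Data analysis plan already promises population estimates with 95% confidence intervals, so the achieved precision will be visible. This bounds the harm to the planning claim.

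**Conclusion.** The concern holds and should be fixed. A design effect of 1 is an unsupported planning input that sits badly with the protocol's own description of the sampling, and the ±5 points at 95% confidence rests on it. At the stated prevalence and N = 580, 186 has almost no room (1.00 to 1.03) and 205 little (1.16 to 1.19). At N = 463 the limit for 205 rises to 1.35 to 1.38.

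The true design effect cannot be known from the documents, so the size of the shortfall is conditional. For an assumed 1.5 to 3, 205 people give about ±5.6 to ±7.9 points with the N = 580 correction and ±7.0 to ±9.9 without. No bias in the prevalence estimate follows, and the interval finally reported from the RDS analysis need not inherit the value 1.

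**What to change.** Amend Target population size as follows.

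1. Keep 205 as a fixed recruitment target and stop presenting it as delivering ±5 points. Do not simply enter a larger design effect in the formula, because 205 would then no longer follow from it.
2. Label the seven-row table as simple-random-sampling values.
3. State an assumed design effect above 1, with its basis and a sensitivity range.
4. Give the expected 95% half-width at 205 over that range, as in step 3 of the working.
5. State whether the finite population correction applies, reconciling the with-replacement theory in Sample design with the rule that repeat participants are not counted.
6. Report the achieved design effect alongside the prevalence.

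The cost is a few sentences, a table label and one extra reported quantity. The stated precision becomes less favourable. No additional participants are needed, and fieldwork and the planned estimation do not change.

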The significance between the relationships will be determined by the p-value of the test, a value less than 0.05, it is accepted that there is a statistical association between the two variables analyzed.

The processing will be carried out in the RDSAT® version 5.6 program.

C. WORK PLAN

Phase 1. Exploratory component

With the purpose of making an approach and identifying barriers to the study and possible alternative solutions to consumption contexts, as well as establishing inter-institutional alliances that facilitate communication with research subjects called seeds, an exploratory phase will be carried out through the use of a qualitative technique that enables the collection and construction of data that enriches the information obtained by the subsequent application of the structured survey that underpins the present study.

We will seek to identify characteristics of the social network: subgroups, connectivity, personal network, the acceptability of the study, interest, possible reasons for not

ID: CO-US-987-7106 - Version May 2024

participating, as well as define logistical aspects, such as the site for collecting information, schedules, coupon design and the profile of the personnel who will serve the prioritized populations.

Through interviews with representatives of various institutions in Armenia who, from research, care, and treatment, offer the research team a general overview of the context and care routes; and from there provide elements that guide field work and the analysis of the information obtained from the surveys.

After prioritizing institutions, they will be inquired about the description of the problem, characterization of the populations, institutional experiences, research, territorial location, methods of approach, risk behaviors and practices for HCV infection, among others. The estimated time to complete the exploratory phase will be two months, this includes the collection, analysis and interpretation of the data and the understanding of the conditions found.

Interviews with key informants

These people are considered experts in the social and cultural context of PWIDs, with the objective of understanding the context and behavior of users; example of key informants: people who have worked with populations, people from institutions, NGOs, among others. In this first phase, the capture technique, already described previously, will also be applied.

Phase 2. Quantitative component

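### Optional, low-cost improvement: the only association method the protocol states for the behaviour objective is an unadjusted pairwise chi-square, which cannot show whether a behaviour stays associated with antibody status at similar age and injecting history

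*Protocol*

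**What the plan says.** Under Type of study the protocol states: "An anonymous, confidential analytical cross-sectional study will be carried out". The General objective is, in part, to "identify the behaviors associated with infection in people between 18 and 65 years of age who inject drugs". The Specific objectives include "Identify behaviors associated with HCV infection among PWID", with no exploratory label, and, as a separate item, "To carry out an exploratory analysis of the association of positive cases and the different risk factors for HCV infection among PWID".

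The Data analysis plan names one method for associations: "a bivariate analysis will be proposed using chi-square tests to explore the proposed associations". The decision rule is "a value less than 0.05, it is accepted that there is a statistical association between the two variables analyzed". The statistic is explained with the sentence "The greater the difference, the greater the relationship between the variables".

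The same section describes the sample "according to the socio-demographic variables: sex, age, educational level, stratum, insurance". It also plans population proportions by risk behaviour with 95% confidence intervals, but no ratio or difference that compares groups. The Variables section lists age, injections per day and number of sharing partners; it does not name years since first injection. Information processing foresees a secondary analysis in Stata and SPSS but names only the packages. No regression, stratification or adjustment variable is stated anywhere in the protocol.

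**The concern.** Antibody status reflects past exposure. Older or longer-term injectors have had more time to become positive, and their current behaviour may also differ from that of newer injectors. A pairwise chi-square combines these two facts. It can flag a behaviour that is tied to infection, or one that only marks longer injecting, and nothing in its output separates the two.

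The report could therefore list a behaviour as associated with infection when the association would vanish among people of similar age and injecting history. Without a comparison measure, the reader would also lack a size for each association. The sentence that equates a larger chi-square difference with a stronger relationship invites use of the test statistic as that size, which it is not.

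**Working it through.** **1. The plan's own figure.** The sample size formula under Target population size, with N = 580, p = 0.778, d = 0.05, z = 1.96 and design effect 1, gives 580 × 0.1727 / [(0.0025/3.8415) × 579 + 0.1727] = 100.17 / 0.5495 = 182.3, so 183. The stated figure is 186, 1.6% higher. Then 186 × 1.10 = 204.6, so 205. This size is set for a prevalence; no power is stated for the association analysis.

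**2. Antibody-negative people expected.** At the planning prevalence of 77.8%: 205 × 0.222 = 45.5. At the 2021 Armenia figure of 69.6% (Problem statement and justification): 205 × 0.304 = 62.3. This smaller class limits the size of any model.

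**3. Illustration of confounding.** From the document: n = 205, the two prevalences and the 0.05 threshold. Assumed: half are long-term injectors, 45% report the behaviour, long-term and other injectors differ by the same gap g in HCV and in the behaviour, and there is no association within either stratum.

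The crude difference in prevalence is 0.5 × 0.5 × g² / (0.45 × 0.55) = 0.25g² / 0.2475. For g = 0.10, 0.20 and 0.30 this is 0.0101, 0.0404 and 0.0909.

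Simulated share of studies with p below 0.05 (4,000 replicates; the adjusted model is a robust Poisson with the confounder included):

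| Gap (points) | Crude difference (points) | Chi-square, prevalence 69.6% / 77.8% | Adjusted, 69.6% / 77.8% |
|---|---|---|---|
| 10 | 1.0 | 5.3% / 5.2% | 4.8% / 4.7% |
| 20 | 4.0 | 9.8% / 11.5% | 4.5% / 5.1% |
| 30 | 9.1 | 27.8% / 34.0% | 5.1% / 5.1% |

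The adjusted prevalence ratio was 1.00 in all six settings.

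Hand check at 20 points and 77.8%: prevalence with the behaviour is 0.778 + 0.55 × 0.0404 = 0.800, without it 0.778 − 0.45 × 0.0404 = 0.760. The groups are 92.25 and 112.75 people. SE = √(0.800 × 0.200/92.25 + 0.760 × 0.240/112.75) = 0.0579, and 0.0404/0.0579 = 0.70. The rejection probability is P(Z > 1.26) + P(Z < −2.66) = 0.104 + 0.004, about 11%, in line with the simulation.

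**4. The statistic is not a measure of strength.** Take two tables of 205 people.
- 23/25 against 131/180: difference 92.0 − 72.8 = 19.2 points. Chi-square = 205 × (23×49 − 2×131)² / (25×180×154×51) = 4.34.
- 82/100 against 71/105: difference 82.0 − 67.6 = 14.4 points. Chi-square = 205 × (82×34 − 18×71)² / (100×105×153×52) = 5.60.

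The weaker association has the larger statistic, because the statistic also depends on the margins and on n. This example needs no assumption about confounding.

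**5. Limits of adjustment, also under assumed inputs.**
- *Age alone.* In a separate simulation injecting duration is continuous, with a 20-point gap between its halves, at 77.8%. The chi-square rate is 17-19%. It exceeds the 10-12% above because a continuous duration also acts within each half. Adjusting for age alone leaves 13.2% or 8.7% at age-duration correlations of 0.5 or 0.7; age plus duration gives 4.9-5.0%.
- *Recruitment dependence.* With no association but clustering of 0.3 in both HCV status and the behaviour along recruitment links, the chi-square rejects in 8.1% (69.6%) and 7.1% (77.8%), and an age-adjusted model in 7.8% and 6.8%. At 0.5 the figures are 14.7% and 13.9% against 14.7% and 13.6%. If only HCV clusters, at 0.5, the chi-square stays at 5.0% and 5.7%. Adjustment does not cure this.
- *Power.* For a true 15-point difference within strata and 10-point confounder gaps: 80.2% (chi-square) against 75.2% (adjusted) at 77.8%, and 71.5% against 67.0% at 69.6%.

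**The case against.** The strongest reply is that nothing stated is wrong. The objectives ask for behaviours associated with infection, the decision rule claims only a statistical association, and the wording of the association paragraph is exploratory throughout. A study called analytical is not thereby committed to multivariable adjustment. This stands. A reader might infer that the chi-square is an invalid test or that the protocol draws causal conclusions; the text supports neither. The rejections in the table detect a real marginal difference and are not errors of the test.

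A second reply is that covariates and models are often left to a statistical analysis plan, which may exist, and that the secondary analysis is not limited to chi-square. This also stands in part: a reader might infer that adjustment is excluded, and it is not. But the protocol has its own Data analysis plan that names the test, the threshold and how to read the statistic, and it is that stated choice which can be improved.

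Third, the rates rest on invented confounder strengths. That is correct. Wider assumed gaps, 24.4 points in HCV (90% against 65.6%) and 40 points in a behaviour reported by half (70% against 30%), give about 39%; gaps of 10 points do no visible harm. The documents do not say where this study lies.

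Fourth, a model brings problems of its own: RDS weights, recruitment dependence and a possibly unrecorded duration. These stand, and the fix must state them so that adjusted intervals do not give false assurance.

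Finally, the sentence on the size of the difference may be only a lay account of the test, and no ranking of variables is planned. That lowers its weight, but as a statement about strength it is still incorrect.

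**Conclusion.** The point holds as a modest, optional improvement. The only association method stated for the behaviour objective is unadjusted and gives no comparison measure. It cannot show whether an association persists among people of similar age and injecting history. Under the stated assumptions the rate of p below 0.05 without any within-stratum association runs from about 5% (10-point gaps) through 10-12% (20) to 28-34% (30). These are hypothetical figures, not a forecast for this study; with weak confounding nothing is gained. The correction about strength needs no such assumption. The antibody prevalence estimate is not affected.

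**What to change.** In the Data analysis plan:

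- Keep the chi-square tests, labelled as unadjusted description.
- Add one small prespecified model per behaviour for antibody status, for example robust Poisson, adjusted for age and for years since first injection if the instrument records it. Confirm that item when the instrument is reviewed before the pilot (Field work, quantitative phase).
- Report adjusted prevalence ratios with 95% CIs; Stata and SPSS are already foreseen.
- State whether the model is unweighted or uses the RDS weights, and report the other version as a sensitivity analysis.
- State that p-values and CIs ignore dependence along recruitment links and may be too narrow if both HCV status and the behaviour show homophily, which the plan already calculates.
- Replace the sentence that equates a greater difference with a greater relationship, and use the prevalence ratio for strength.

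The cost is some analysis time, more with the weighted version, and at most one survey item; no extra participants are needed. The downsides are these: models must stay small, with about 45 to 62 antibody-negative people expected; about 5 points of power are lost for a true effect in the setting above; age alone controls confounding only in part if years injecting is not recorded; and recruitment dependence remains, hence the stated caveat.
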